3.10 Visit Windows

It is expected that all visits should occur according to the protocol schedule within the allowed protocol-specified window. All data will be tabulated per the evaluation visit as recorded on the eCRF even if the assessment is outside of the protocol-specified visit window. For the Week 12 visit (Visit 6), an analysis window will be created with a larger interval to allow in-person unscheduled visits within the interval to act as the nominal Week 12 visit; the analysis window will consist of the target day, plus or minus 14 days. For any other visit, if an unscheduled visit occurs within the allowed protocol-specified window and there are no scheduled visits reported, the unscheduled visit may act as the planned visit. If there are multiple visits in a same visit window, the median value will be used for analysis.

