9.0 Efficacy figures

The following response rates, using the primary analysis methods and estimand framework, where applicable, with 95% confidence intervals will be plotted over time, with separate curves for the initial 12-week period and the 12-week maintenance period:

- IGA (combined scale and fissuring) ≥ 2 grade improvement
- IGA (combined scale and fissuring) score of 0 or 1
- IGA (scaling) ≥ 2 grade improvement
- IGA (fissuring) ≥ 2 grade improvement
- ≥ 4 -point improvement in WI-NRS, among subjects with baseline WI-NRS ≥ 7
- ≥ 4 -point improvement in WI-NRS, among subjects with baseline WI-NRS ≥ 4
- ≥ 50 percent reduction in the average VIIS scaling score, among all treated areas with a baseline VIIS-scaling score ≥ 3
- ≥ 25 percent reduction in the average VIIS scaling score, among all treated areas with a baseline VIIS-scaling score ≥ 3
- ≥ 4 -point reduction in DLQI, among adult subjects with baseline score ≥ 11
- ≥ 4 -point reduction in DLQI, among adult subjects with baseline score ≥ 4
- ≥ 4 -point reduction in CDLQI, among pediatric subjects with baseline score ≥ 13
- ≥ 4 -point reduction in CDLQI, among pediatric subjects with baseline score ≥ 4
- ≥ 11 -point change from baseline in IQOL-32

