3.0 GENERAL ANALYSIS CONVENTION

3.1 Timing of Analyses

Analysis of topline data will be performed once all subjects complete their Week 12 (Visit 6) visit, and that all data up to that point are entered and locked within the database. Topline data minimally consists of the primary and key secondary efficacy endpoints; other disposition, demographic, safety, and efficacy parameters may be provided as well.

All remaining analyses will be performed when all subjects have either completed the study or discontinued early from the study, and all data from the study are in the clinical database, and the database is locked.

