3.9 Missing Data Handling

3.9.1 Efficacy Data

Missing data for the primary, key secondary efficacy endpoints, and select other secondary endpoints will be handled by a multiple imputation model containing baseline values, post-baseline values collected at an in-person visit (i.e. not collected remotely), treatment (TMB-001 0.05% or Vehicle for the Week 12 endpoints, TMB-001 0.05% BID or QD for the Week 24 endpoints), and randomization stratification factors. Imputation of missing data will be conducted under a working assumption of missing at random (MAR), meaning that the propensity for a data point to be missing is not related to the missing data, but it is related to some of the observed data. The following steps will be taken:

- 1) For all scores, the missingness pattern in the data will be evaluated. If the pattern is not monotone, the MCMC method of SAS PROC MI will be used to make it monotone. The minimum values for imputed variables will be set to 0, in order to force PROC MI to redraw another value for imputation when an intended imputed value is less than the 0. For IGA scores (including scaling and fissuring sub-scores) and the VIIS scores, the maximum value for imputed variables will be set to 4, in order to force PROC MI to redraw another value for imputation when an intended imputed value is greater than the 4. For the I-

NRS/WI-NRS, the maximum value for imputed variables will be set to 10. Imputed values will be rounded to the nearest integer.

- 2) SAS PROC MI will be used for imputing missing values of data with monotone missing pattern. If the MCMC method of step 1 was previously employed, one imputation will be made using each of the 50 MCMC-imputed datasets. If the MCMC method of step 1 was not previously employed, 50 imputations will be created assuming the data are missing at random (MAR).
- 3) A linear regression model will be used to impute all scores individually, using the treatment arm and non-missing scores from earlier scheduled timepoints. All response statuses will be calculated from the imputed scores.

The resulting analysis of the multiply imputed data will be outlined in Section 5.

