5.1.2 Primary Analysis Methods

The difference in proportion of subjects achieving IGA treatment success at Week 12 (Visit 6) between the TMB-001 0.05% and vehicle groups will be the primary efficacy endpoint. For this endpoint, the IGA score will be dichotomized to "responder" (treatment success) or "non-responder" (treatment failure), where a responder is defined as at least a 2-grade improvement (decrease) in severity in the IGA score as compared to baseline. Inference will be made by comparing the proportions of

treatment successes in the TMB-001 0.05% group vs the vehicle group at Week 12 using the CMH test stratified by age (≥ 17 , 12-16 and 6-11) and genetic subtype. A two-sided alpha of 0.01 will be used for significance testing, along with 99% and 95% confidence intervals.

Missing Week 12 data will be imputed, as outlined in Section 3.9.1, and IGA responder status will be derived from the imputed values. A CMH analysis will be performed on each of the 50 imputed datasets. The results from the CMH analyses will be combined using the Wilson-Hilferty transformation by Ratitch et al. (Ratitch et al. 2013) to produce a pooled CMH statistic and p-value. The differences in proportions and standard errors will be combined using Rubin's Rule (Little 2019) the SAS PROC MIANALYZE. The pooled Mantel-Haenszel stratum-weighted estimator of the difference in proportion and the associated standard error will be used to produce the 99% confidence interval based on the large-sample approximation method for binary data without using continuity correction. The 95% confidence interval will also be provided.

A summary of the occurrences of intercurrent events of each type will be provided by treatment group.

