5.2.2 Analysis Methods

Statistical testing will be performed on the key secondary efficacy endpoints using a two-side alpha of 0.01, according to the following hierarchical order.

5.2.2.1 IGA Clear Score Responders at Week 12

The difference in proportions of subjects with IGA score of clear or almost clear (henceforth referred to as 'IGA clear score responders') versus mild/moderate/severe will be computed at Week 12, between the TMB-001 0.05% and vehicle treatment groups.

The difference in proportions will be calculated in a similar manner as the primary efficacy endpoint using the CMH test, including the use of 50 multiply imputed datasets combined using the Wilson-Hilferty transformation for the pooled CMH statistic and Mantel-Haenszel stratum-weighted difference in proportions combined using Rubin's rule. Results will be provided using the primary efficacy data presentation.

5.2.2.2 IGA-Scaling Sub-Score Responders at Week 12

The difference in proportions of subjects with a ≥ 2 point change from baseline in IGA-scaling severity sub-scores (henceforth referred to as 'IGA-scaling sub-score responders') will be computed at Week 12 among subjects who have a score of ≥ 3 at baseline, between the TMB-001 0.05% and vehicle treatment groups.

The difference in proportions will be calculated in a similar manner as the primary efficacy endpoint using the CMH test, including the use of 50 multiply imputed datasets combined using the Wilson-Hilferty transformation for the pooled CMH statistic and Mantel-Haenszel stratum-weighted difference in proportions combined using Rubin's rule. Results will be provided using the primary efficacy data presentation.

5.2.2.3 Worst Itch-QoL (WI-NRS) Responders at Week 12

The difference in proportions of subjects achieving a ≥ 4 -point improvement from baseline in weekly Worst Itch-QoL scores on the WI-NRS (henceforth referred to as 'Worst Itch-QoL (WI-NRS) responders') will be computed at Week 12, between the TMB-001 0.05% and vehicle treatment groups. Only subjects with baseline WI-NRS scores of ≥ 7 will be included in this analysis.

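### SAP 3.10 gives Visit 6 no precedence in the Week 12 window and no cut-off at the Period 3 switch, so an extra or post-switch IGA can change primary responder status

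*SAP*

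**What the plan says.** SAP 3.10 first sets a general rule: data are tabulated by the visit recorded on the eCRF, even when the assessment is out of window. It then makes three further statements.

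- For Week 12 (Visit 6) only, a wider window lets in-person unscheduled visits act as the nominal visit: "the analysis window will consist of the target day, plus or minus 14 days". Nothing requires Visit 6 to be absent.
- The next sentence does contain such a requirement, but it begins "For any other visit, if an unscheduled visit occurs within the allowed protocol-specified window and there are no scheduled visits reported". It therefore covers every visit except Week 12.
- The last sentence has no exception: "If there are multiple visits in a same visit window, the median value will be used for analysis".

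The window feeds the primary endpoint, where "a responder is defined as at least a 2-grade improvement (decrease) in severity in the IGA score as compared to baseline" (SAP 5.1.2). It also feeds two key secondary endpoints. One is clear or almost clear, which section 9.0 of the SAP addendum words as "IGA (combined scale and fissuring) score of 0 or 1". The other is the scaling sub-score response, analysed "among subjects who have a score of ≥ 3 at baseline".

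At Week 12, TMB-001 subjects with at least a 1-point improvement move to open-label BID or QD, and vehicle subjects with less than a 1-point improvement may cross over to TMB-001 BID (Protocol 4.1, SAP 1.3.1). Protocol 8.2.1 allows a remote Visit 6 IGA when a physical restriction on travel is documented.

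**The concern.** Two things are left open for the assessment that carries the primary endpoint.

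**Precedence.** The author wrote a precedence condition for all other visits but not for this one. Two programmers working in good faith could derive different responder flags for the same subject. One would use Visit 6 alone; the other would take the median of Visit 6 and an unscheduled score. A median of two grades can be a half-grade, which is not a point on the IGA scale. SAP 3.9.1 has a rounding rule, but only for imputed values.

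**Cut-off.** The window runs past the point at which treatment changes. A score obtained on open-label TMB-001, including in a former vehicle subject, can be counted in a comparison that is meant to be blinded and vehicle-controlled.

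The estimand (SAP 5.1.1) and the sensitivity analyses (SAP 5.1.3) do not deal with which visit supplies the Week 12 score, so none of the planned analyses would show the difference between readings.

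**Working it through.** **Window.** The target is Day 84 with a protocol window of ±7 days (Protocol Table 1).

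- Protocol window for Visit 6: 84 − 7 = 77 to 84 + 7 = 91.
- SAP 3.10 analysis window: 84 − 14 = 70 to 84 + 14 = 98.
- Days in the window after Visit 6: 98 − 77 = 21 (earliest Visit 6), 98 − 84 = 14 (on target), 98 − 91 = 7 (latest). These are Period 3 days if Period 3 dosing starts at Visit 6.

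The protocol numbers Baseline as Day 0 and the SAP numbers first dose as Day 1, so in SAP study days the window may read Day 71 to 99. This changes nothing below.

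**Literal reading, one extra visit.** Baseline IGA is 3 or 4 (Protocol 5.1, criterion 7). With Visit 6 and one extra score each running from 0 to 4, there are 2 × 5 × 5 = 50 combinations. The median of two scores is their mean. A subject is a primary responder if baseline minus median is at least 2, and clear or almost clear if the median is at most 1. Combinations are written baseline/Visit 6/extra.

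| Endpoint | Responder lost | Responder gained |
|---|---|---|
| Primary | 8: 3/0/3, 3/0/4, 3/1/2, 3/1/3, 3/1/4, 4/1/4, 4/2/3, 4/2/4 | 4: 3/2/0, 4/3/0, 4/3/1, 4/4/0 |
| Clear or almost clear | 10: 3/0/3, 3/0/4, 3/1/2, 3/1/3, 3/1/4, 4/0/3, 4/0/4, 4/1/2, 4/1/3, 4/1/4 | 2: 3/2/0, 4/2/0 |

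The primary grid also applies to the scaling sub-score, which is restricted to baseline 3 or more. These are counts of possible combinations, not probabilities.

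A one-grade disagreement is enough. For 3/1/2 the median is (1 + 2)/2 = 1.5 and the improvement is 3 − 1.5 = 1.5, below 2; 1.5 is also above 1. Of the 16 combinations that differ by one grade, 2 lose a responder on the primary endpoint (3/1/2, 4/2/3), 2 lose one on clear or almost clear (3/1/2, 4/1/2), and none gains one.

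**Post-switch scores, by arm.**

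- TMB-001 subjects eligible for Period 3 (improvement of at least 1 at Visit 6) occupy 35 combinations: 8 lost, 3 gained on the primary endpoint.
- Vehicle subjects eligible to cross over (improvement below 1) occupy 15 combinations: 0 lost, 1 gained (4/4/0). With two later scores the route is wider: baseline 3 with both at most 1, or baseline 4 with both at most 2.

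**Substitution reading.** If an unscheduled visit counts only when Visit 6 is not usable, no median with Visit 6 arises. But if a remote Visit 6 is treated as not usable, a later in-person score can replace it, with no limit at the start of Period 3. A vehicle subject with baseline 3 and a remote Visit 6 of 3 crosses over; an in-person score of 1 inside the window then gives 3 − 1 = 2, a vehicle responder.

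**Weight of one subject.** With 110 subjects at 2:1, about 73 and 37, one subject is 1/73 = 1.4 percentage points on TMB-001 or 1/37 = 2.7 points on vehicle. How many subjects are affected cannot be computed: the documents give no count of in-person unscheduled visits with an IGA in the window.

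**The case against.** The strongest reply is that substitution is what the text means. A visit need not act as Visit 6 when Visit 6 exists. SAP 3.10 tabulates by eCRF visit and names the window as Visit 6, and SAP 5.1.2 places the primary endpoint at Week 12 (Visit 6). The median sentence follows one about stand-in visits, so it may only concern several stand-ins. On the switch, Protocol 10.3.1.1.2 ties the key secondary endpoints to Periods 1 and 2, SAP 8.0 records no departure from that, SAP 3.11.2 presents Period 3 separately, and addendum 9.0 plots separate curves for the two 12-week periods.

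Most of this stands as evidence of intent. None of it ranks Visit 6 above an unscheduled visit or sets a last admissible date, and the remote Visit 6 route survives the substitution reading.

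The reply is also right that duplicates should be rare. Visit 5 falls on Day 49 to 63 and Visit 7 on Day 105 to 119, so a duplicate needs an extra in-person visit with an IGA graded.

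A reader might go further and infer that scores will be combined, that crossover biases the vehicle arm, or that power falls. The documents do not support these inferences. The text permits combination without showing it is planned. With one extra score, a crossover subject becomes a responder under the literal reading only at 4/4/0. Losing TMB-001 responders and losing vehicle responders move the treatment difference in opposite directions, and no document says how many of either would change.

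**Conclusion.** The point holds as a gap in a stated rule for the primary endpoint. Followed as written, SAP 3.10 can put a half-grade or a post-switch open-label score into Week 12 responder status. Substitution was probably intended, but the text does not say so, and even substitution leaves the window open after the switch when Visit 6 was remote.

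The size is unknown and probably small. The 21-day figure is the extreme case: Visit 6 on Day 77, Period 3 dosing from that visit, and an extra IGA on Day 98. No direction of bias and no change in power can be claimed. It should still be fixed, because choosing between readings after unblinding would be a post hoc decision about the primary endpoint.

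**What to change.** In SAP 3.10, for the Week 12 IGA endpoints (combined score and sub-scores), state that:

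1. a usable Visit 6 value is used alone;
2. an in-person unscheduled assessment within Day 70 to 98 may stand in only when there is no usable Visit 6 value, and whether a remote Visit 6 permitted by Protocol 8.2.1 counts as usable;
3. a stand-in must have been taken on or before the first Period 3 application, a date already defined in SAP 7.1.

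Leave the median rule for several stand-in visits, and the rules for VIIS, WI-NRS and other visits, as they are; no defect is shown there.

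The cost is two or three sentences and a small change to the derivation. The downside is that a few Week 12 values may become missing and be imputed under SAP 3.9.1.

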3.11 Data Presentation

3.11.1 Disposition, Demographics, and Baseline Characteristics

Disposition, demographics, and baseline characteristics data for all subjects (including those enrolled in the optional maximal use arm) will be pooled for analysis.

TMB-001 0.05% (N=xx)	Vehicle (N=xx)	Phase 3 Overall (N=xx)	Maximal Use Arm (N=xx)	Overall (N=xx)
----------------------------	-------------------	------------------------------	------------------------------	-------------------

This data presentation will be used for all analyses described in Section 4 below.

3.11.2 Efficacy

Efficacy data for all subjects will have two presentations, depending on the endpoints being analyzed. For the primary, key secondary, and select other secondary efficacy endpoints, the data presentation (henceforth referred to as 'primary efficacy data presentation') will have the following header:

TMB-001 0.05% (N=xx)	Vehicle (N=xx)
----------------------------	-------------------

For endpoints analyzed on parameters collected during Period 3, a secondary data presentation will be used (henceforth referred to as 'open-label dosing efficacy data presentation'), with the following header:

	OL TMB-001 0.05% BID (N=xx)		
OL TMB-001 0.05% QD (N=xx)	TMB-001 0.05% in Blinded Phase (N=xx)	Vehicle in Blinded Phase (N=xx)	Total OL TMB- 001 0.05% BID (N=xx)

An overall column is not planned for any efficacy output, however it may be added, if warranted.

3.11.3 Safety

The primary data presentation for all safety analyses (henceforth referred to as 'primary safety data presentation') will have the following table header:

TMB-001 0.05% (N=xx)	Vehicle (N=xx)	Overall (N=xx)
----------------------------	-------------------	-------------------

The TMB-001 0.05% and Vehicle columns will represent the subjects initially randomized to either TMB-001 0.05% or vehicle, regardless of the second randomization allocation in Period 3.

Additionally, a data presentation specific to Period 3 will be used:

	OL TMB-001 0.05% BID (N=xx)			
OL TMB-001 0.05% QD (N=xx)	TMB-001 0.05% in	Vehicle in Blinded	Total OL TMB- 001 0.05% BID (N=xx)	Overall (N=xx)

	Blinded Phase (N=xx)	Phase (N=xx)		
--	-------------------------	-----------------	--	--

This data presentation (henceforth referred to as 'open-label dosing safety data presentation') will be used for all analyses of safety endpoints specifically during Period 3, comparing TMB-001 0.05% BID and QD maintenance dosing.

3.12 Interim Analysis

There is no interim analysis planned for this study.

4.0 DISPOSITION, PROTOCOL DEVIATIONS, DEMOGRAPHICS AND BASELINE ANALYSES

All analyses in this section will be performed using the Safety Population and presented using the data presentation described in Section 3.11.1, unless otherwise indicated.

4.1 Disposition

Subject disposition will be tabulated by treatment group and overall, based on all subjects screened. The number of subjects and percentages will be provided for the number screened, the number randomized, the number treated, the number re-randomized in Period 3, the number in each analysis population, the number who completed each period, the number who completed the study, the number who withdrew prior to completion and the reason(s) for withdrawal.

A by-subject data listing of disposition data will be provided, including a separate data listing for inclusion/exclusion information.

4.2 Demographics and Baseline Characteristics

Demographics and baseline characteristics will be tabulated and will be summarized using descriptive statistics. Variables include: age (years), sex, race, ethnicity, height, weight, and BMI. All variables will be reported as collected in the eCRFs except for BMI, which will be computed using height and weight such that $BMI = \text{weight (kg)} / [\text{height (m)}]^2$. Demographic and baseline data for each subject will be provided in data listings.

Demographics and baseline characteristics summaries will be provided for the ITT and PP Populations in addition to the Safety Population.

Medical history will be coded using MedDRA v25.0 and presented by system organ class and preferred term. If a subject had more than one medical history event within a system organ class, the subject is counted once for each preferred term and once for the system organ class. The table will be sorted by descending frequency, based on the overall column of the data presentation. Medical history data will also be provided in a by-subject listing.

A by-subject listing of pregnancy test results will be provided.

4.3 Baseline Disease Characteristics

The type of CI (both as reported in the IRT and in the EDC) and specific mutation will be tabulated, in addition to whether the test was performed prior to or as part of the screening portion of the study. The time since initial clinical diagnosis of CI, as well as

the total percent body surface area (BSA) affected with CI will be summarized using descriptive statistics.

Prior medications specific for the treatment of CI will be tabulated, such as the use of over-the-counter products and emollients, oral retinoids, UV light, systemic corticosteroids, and topical retinoids.

All baseline disease characteristics will be provided in by-subject data listings.

4.4 Protocol Deviations

All protocol deviations that could compromise the interpretation of efficacy or safety of the study drug will be considered as major deviations. The Sponsor will be responsible for approving the final protocol deviation; this file will include a description of the protocol deviations and clearly identify whether this deviation warrants exclusion from the PP Population. This file will be finalized prior to database lock/unblinding for the execution of the primary analysis.

A summary tabulation of major protocol deviations will be provided. All protocol deviations will be presented in a by-subject data listing.

4.4.1 Deviations Related to COVID-19

Protocol deviations due to COVID-19 will be reported in a separate by-subject data listing. All visits and assessments impacted by COVID-19 will be listed.

5.0 EFFICACY ANALYSIS

5.1 Primary Efficacy

All analyses in this section will be presented as described in Section 3.11.2, unless otherwise indicated.

All source data for all efficacy parameters will be provided in by-subject data listings.

All efficacy measurements over time will also be tabulated using descriptive statistics, as well as presented graphically using by-subject line plots, where only those subjects who are eligible to be responders will be provided.

